16.1.7.3. Hypersensitivity Reactions

Hypersensitivity reactions are those events recorded as MedDRA code in the pre-defined Standardized MedDRA Queries (SMQ) "Hypersensitivity" (narrow).

Hypersensitivity reaction adverse events of special interest (Hypersensitivity reactions AESI) are those events both identified as Hypersensitivity reaction adverse events and recorded as "Adverse Event of Special Interest" equal to "Yes" on the Adverse Events page of the eCRF.

Hypersensitivity reactions will also be listed. The listing will include the "Adverse Event of Special Interest" equal to "Yes" information from the Adverse Events page of the eCRF as a flag.

16.1.7.4. Drug Induced Liver Injury (DILI)

Drug Induced Liver Injury (DILI) are those events identified by medical advisor on the subset of AEs for subjects presenting laboratory potential DILI findings (refer to section 16.3).

DILI events of special interest (DILI AESI) are those events both identified as DILI adverse events and recorded as "Adverse Event of Special Interest" equal to "Yes" on the Adverse Events page of the eCRF.

Drug Induced Liver Injury (DILI) will be listed. The listing will include the "Adverse Event of Special Interest" equal to "Yes" information from the Adverse Events page of the eCRF as a flag.

16.1.7.5. Injection-site reactions

Injection-site reactions are those events recorded with MedDRA high level terms (as listed in BICMQs

Administration site reaction subsearches 1,2,4 and 5, with a version consistent with the MedDRA version, refer to APPENDIX 4):

- Administration site reactions NEC
- Application and instillation site reactions
- Infusion site reactions
- Injection site reactions

These will be presented by period and treatment.

There are 2 periods:

Document: \\ieedc-
vnasc01\BIOSdata\Boehringer_Ingelheim\BI_695501\NVA96252\Biostatistics\Documentation\S
AP\BI1297.4 SAP FINAL v4.0_22MAY2019.docx

Author: Version Number: Final V4.0
Version Date: 22MAY2019

Template No: CS_TP_BS016 Revision 5
Effective Date: 01Apr2018

Reference: CS_WI_BS005

Period 1	Visit date within [first injection date; Week 24 Visit[+10 weeks (70 days) inclusive (for patients that discontinued the treatment before week 24).
Period 2	Visit date within 
 • [Week 24 Visit; Week 56 Visit[or • [Week 24 visit; last injection date + 10 weeks (70 days)] (for patients that discontinued the treatment before week 56)].

Injection-site reactions will be listed.

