- Contact IRT and administer trial medication

At Visit 14, patients initially randomized to EU-approved Humira will switch to receive BI 695501. From Visit 14 onwards, all patients will be receiving BI 695501.

Page 59 of 93

Proprietary confidential information © 2017 Boehringer Ingelheim International GmbH or one or more of its affiliated companies

Visits 6, 10, 18 and 22 (Days 57, 113, 225 and 281, respectively)

The following will be performed/collected:

- Vital signs (blood pressure, pulse rate, and body temperature; see Section 5.3.2)
- Laboratory testing (serum chemistry, hematology, and urinalysis; see Section 5.3.3)
- Urine pregnancy test for women of childbearing potential
- 12-lead ECG (Visit 6 only; see Section 5.3.4)
- Previous and concomitant therapy (see Section 4.2)
- Assessment of AEs (see Section 5.3.6)
- Contact IRT and administer trial medication

Visit 8 (Day 85)

The following will be performed/collected:

- Vital signs (blood pressure, pulse rate, and body temperature; see Section 5.3.2)
- Previous and concomitant therapy (see Section 4.2)
- Assessment of AEs (see Section 5.3.6)
- Evaluation of CDAI (see Section 5.2.1)
- Contact IRT and administer trial medication

At this visit, the hematocrit value from the central laboratory assessment at Visit 6 (Day 57) will be used to determine CDAI score.

Visits 12 and 16 (Days 141 and 197, respectively)

The following will be performed/collected:

- Vital signs (blood pressure, pulse rate, and body temperature; see Section 5.3.2)
- Previous and concomitant therapy (see Section 4.2)
- Assessment of AEs (see Section 5.3.6)
- Contact IRT and administer trial medication

Trial medication administration only visits

Visits 5, 7, 9, 11, 13, 15, 17, 19, 20, 21, 23, 24, and 25 are for administration of trial medication only and the following will be performed:

• Contact IRT and administer trial medication

Page 60 of 93

Proprietary confidential information © 2017 Boehringer Ingelheim International GmbH or one or more of its affiliated companies

End of Treatment Visit

The following will be performed/collected:

- TB test (IGRA e.g., QuantiFERON[®] Gold assay)
- Physical examination, including weight (kg) (see Section 5.3.1)
- Vital signs (blood pressure, pulse rate, and body temperature; see Section 5.3.2)
- Laboratory testing (serum chemistry, hematology, and urinalysis; see Section 5.3.3)

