16.1.1. ADVERSE EVENT SPECIFIC DERIVATION

16.1.1.1. Treatment Emergent Adverse Event

Treatment-Emergent Adverse Events (TEAEs) are defined as AEs that started or worsened on or after the first dose of trial medication and prior to the last date of trial medication + 10 weeks (70 days) inclusive.

There are two specific periods of interest:

Period 1 Treatment-Emergent Adverse Events (P1 TEAEs) are defined as AEs that started or worsened on or after the first dose of trial medication and prior to the date of Week 24 visit or within 10 weeks (70 days, inclusive) after the last dose of IMP for patients who discontinued the treatment before Week 24.

Period 2 Treatment-Emergent Adverse Events (P2 TEAEs) are defined as AEs that started or worsened on Week 24 visit and prior to or on the Week 56 visit or within 10 weeks (70 days, inclusive) after the last dose of IMP for patients discontinuing treatment prior to Week 46.

Non-TEAEs will be classified as "Screening" if AE start date is strictly prior to the first injection date. Non-TEAEs will be classified as "Post treatment" if AE start date is strictly after the last injection date + 70 days.

See APPENDIX 2 for handling of partial dates for AEs. In the case where it is not possible to define an AE as treatment-emergent or not, the AE will be classified by the worst case, i.e., treatment-emergent in the period of the last injection of trial medication.

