16.1.2. ALL TEAEs

Number of subjects, percentages, and number of events overall and for period 1 and period 2 will be presented by SOC and PT and also broken down further by maximum intensity and relationship to trial medication.

Periods for TEAE's:

Period 1	Visit date within 
 • [first injection date; Week 24 Visit] or • [first injection date; last injection date + 10 weeks (70 days)] (for patients that discontinued the treatment before week 24)].
Period 2	Visit date within 
 • [Week 24 Visit; Week 56 Visit[or • [Week 24 visit; last injection date + 10 weeks (70 days)] (for patients that discontinued the treatment before week 56)].

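### SAP 16.1.2 and 16.1.7.5 place adverse events in Period 1 or 2 by visit date, in conflict with the onset rule of SAP 16.1.1.1 and with protocol 7.3.4; the SAP does not say which governs

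*SAP*

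**What the plan says.** The SAP gives the period rule three times.

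- **SAP 16.1.1.1** works from event onset: "Period 1 Treatment-Emergent Adverse Events (P1 TEAEs) are defined as AEs that started or worsened on or after the first dose of trial medication", with the upper limit "prior to the date of Week 24 visit". The second period mirrors it: "Period 2 Treatment-Emergent Adverse Events (P2 TEAEs) are defined as AEs that started or worsened on Week 24 visit".
- **SAP 16.1.2** promises the main tables by period: "Number of subjects, percentages, and number of events overall and for period 1 and period 2 will be presented by SOC and PT". The table beneath defines each period by visit date. Its Period 1 interval, "first injection date; Week 24 Visit", is printed with a closed bracket at Week 24, and its Period 2 interval also starts with that visit included.
- **SAP 16.1.7.5** gives a separate period table for injection-site reactions, again by visit date: "Visit date within [first injection date; Week 24 Visit[+10 weeks (70 days) inclusive". The bracket after Week 24 excludes that visit from Period 1. Period 2 is "Week 24 Visit; Week 56 Visit", with Week 24 included.

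Protocol 7.3.4 attributes events around the switch by when they occur. An event that precedes the first BI 695501 dose belongs to the treatment the patient was then receiving. SAP 3.3 declares no change from the protocol analysis.

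**The concern.** Onset date and visit date are different variables. A programmer building the injection-site reaction table has a definition in 16.1.7.5 itself and has no instruction to use 16.1.1.1 instead.

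The stake is the description of the switch from EU-approved Humira to BI 695501, which protocol 2.1 and 3.2 name among the trial's purposes. Period 1 and Period 2 are the pre-switch and post-switch windows. In the Humira arm, a reaction to Humira that is tabulated in Period 2 looks like a reaction arising after the change to BI 695501. In the BI 695501 arm the same rule only moves the timing, because both periods are on the same product.

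**Working it through.** **Inputs**

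- Humira dosing visits before the switch: Weeks 0, 2, 4, ..., 22 (protocol 4.1.1), so 22/2 + 1 = 12 occasions.
- Adverse event assessments after first dose, up to the switch: Weeks 2, 4, 8, 12, 16, 20 and 24 (flow charts; protocol 6.2.2).
- Week 22 is Visit 13, a dosing-only visit: "Visits 5, 7, 9, 11, 13, 15, 17, 19, 20, 21, 23, 24, and 25 are for administration of trial medication only".
- Assessments come before the injection on dosing days (protocol 6.1).
- Week 20 is Day 141 and Week 24 is Day 169 (Flow Chart B).

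**Step 1: which doses are first followed by the Week 24 assessment?** Because assessments are pre-dose, a reaction to the dose at week w first meets a scheduled assessment at the next assessment week after w.

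| Dose week | Next scheduled assessment |
|---|---|
| 0 | 2 |
| 2 | 4 |
| 4, 6 | 8 |
| 8, 10 | 12 |
| 12, 14 | 16 |
| 16, 18 | 20 |
| 20, 22 | 24 |

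Two doses, Weeks 20 and 22, map to Week 24. That is 2/12 = 16.7% of pre-switch dosing occasions. The gap between assessments is 169 − 141 = 28 days, or 22 to 34 days if the two visits move in opposite directions within their ±3-day windows.

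The share depends on the unit counted. With four syringes on Day 1, two on Day 15 and one at each of the ten later visits, there are 4 + 2 + 10 = 16 syringes before the switch, so the exposed share is 2/16 = 12.5%. Of the ten 40 mg doses from Week 4 to Week 22, it is 2/10 = 20%.

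**Step 2: one case under each rule.** Take a Humira patient dosed at Week 22 (Day 155), with a reaction starting on Day 157 and first recorded at the Week 24 visit on Day 169, before the first BI 695501 injection.

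| Rule | Dating variable, read literally | Week 24 visit belongs to | Where the event goes |
|---|---|---|---|
| SAP 16.1.1.1 | onset or worsening | Period 2 | Period 1 (onset Day 157) |
| SAP 16.1.2, as printed | visit date | both periods | both periods |
| SAP 16.1.7.5 | visit date | Period 2 | Period 2 only |
| Protocol 7.3.4 | occurrence relative to first BI 695501 dose | not applicable | Humira |

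**Step 3: the other possible reading.** If visit date was meant as event date, the Day 157 reaction falls in Period 1 under both tables and the conflict over this case disappears. The printed closed bracket in 16.1.2 would still put an event starting on Day 169 into both periods.

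**Step 4: what onset dating leaves open.** SAP 16.1.1.1 sends every onset on the Week 24 visit date to Period 2. Protocol 7.3.4 divides at the first BI 695501 dose, so an event that began earlier that day, before the injection, belongs to Humira. Onset dating alone does not settle that day.

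**The case against.** The strongest reply is that the SAP already has an onset rule and the tables are loosely worded. Section 16.1.1.1 is the derivation section. Appendix 2 decides treatment emergence from the start date. SAP 16.1 opens a new record with its own start date when an event worsens. Protocol 8.3.1 makes onset date mandatory, and no section says that an adverse event record carries a reporting-visit date. This stands in part: misallocation is a risk, not a certainty. It does not remove the need to reconcile three texts that define the same two periods differently. The closed bracket in 16.1.2 may also be a misprint or a product of reading the PDF.

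The impact is limited too. Safety is descriptive, with no between-group comparison unless a section specifies one (SAP 16). The overall tables do not use the periods, both arms share one visit schedule, and the listing of reactions lets a reader check onset. Adverse events are collected continuously from consent, and patients attend for the Week 22 injection, so a Week 20 reaction may well be recorded before Week 24.

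A reader might infer three stronger things that the documents do not support.

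- **That the rule produces a rise in reactions after the switch.** Counted by occasions, 12 and 12 would become 10 and 14, a ratio of 1.40. Counted by syringes, 16 and 12 become 14 and 14, a ratio of 1.00. The apparent rise therefore depends on the unit, as well as on an assumed risk per injection and on reporting only at scheduled assessments.
- **That the same shift occurs for all treatment-emergent events.** As printed, 16.1.2 double counts at Week 24. Both tables also exclude the Week 56 visit from Period 2, so read literally, events first reported there would drop out.
- **That visit dating misplaces these reactions wherever the boundary lies.** It does not. If the Week 24 visit belonged to Period 1 only, a pre-dose report at that visit would be placed correctly.

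**Conclusion.** The SAP contains conflicting rules for placing events in Period 1 or Period 2 and does not rank them. Followed literally, 16.1.7.5 puts Humira reactions first reported at Week 24 into the post-switch period, and 16.1.2 as printed puts them into both. Each result departs from 16.1.1.1 and from protocol 7.3.4, although SAP 3.3 announces no departure.

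The exposure is at most 2 of 12 pre-switch dosing occasions. This assumes that visit date means the visit at which the event is reported and that reporting waits for the scheduled assessment. These are scheduled doses, not events; the number of events affected, and so any change in the period rates, cannot be derived from the documents. The primary efficacy analysis and the overall safety tables are untouched. The point merits correction because the affected display concerns a secondary safety endpoint on either side of the switch.

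**What to change.** 1. In the period tables of SAP 16.1.2 and 16.1.7.5, replace visit date by the date the adverse event began or worsened, as in 16.1.1.1.
2. Use one half-open bracket convention at Week 24 in both tables, so that no event falls in both periods.
3. Assign events starting on the Week 24 visit day by whether they began before or after that day's injection, in line with protocol 7.3.4, and carry the same sentence into 16.1.1.1.

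The first two changes are wording only: onset date is already mandatory, and a worsening already has its own start date. The third needs the order of onset and injection on a single day. The documents do not say whether onset time is recorded, so the SAP should also state a default for when the order is unknown.

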16.1.7.6. Anaphylactic reactions

Anaphylactic reactions are those events recorded as MedDRA code in the pre-defined Standardized MedDRA Queries (SMQ) = "Anaphylactic reactions" (narrow)

Anaphylactic reaction adverse events of special interest (Anaphylactic reaction AESI) are those events both identified as Anaphylactic reactions and recorded as "Adverse Event of Special Interest" equal to "Yes" on the Adverse Events page of the eCRF.

Anaphylactic reactions will also be listed. The listing will include the "Adverse Event of Special Interest" equal to "Yes" information from the Adverse Events page of the eCRF as a flag.

16.1.8. AEs OCCURRING AFTER THE LAST INJECTION FOR SUBJECTS DISCONTINUED DUE TO LACK OF EFFICACY

Subjects who discontinued treatment due to lack of efficacy will be identified from "End of treatment visit" eCRF page, where "Reason for End of Treatment" is "Progressive Disease".

Number of subjects, percentages, and number of events occurring after the last injection and prior to the last injection + 10 weeks for subjects discontinued due to lack of efficacy by SOC and PT will be prepared.

AEs occurring after the last injection and prior to the last injection + 10 weeks for subjects discontinued due to lack of efficacy will be listed.

Document: \\ieedc-vnasc01\BIOSdata\Boehringer_Ingelheim\BI_695501\NVA96252\Biostatistics\Documentation\SAP\BI1297.4 SAP FINAL v4.0_22MAY2019.docx

Author: Version Number: Final V4.0
Version Date: 22MAY2019

Template No: CS_TP_BS016 Revision 5 Reference: CS_WI_BS005
Effective Date: 01Apr2018

16.2. DEATHS

If any subjects die during the trial as recorded on the “End of Treatment” page or the “Trial Completion” page or the AE page (SAE which “Results in death” or AE with “Fatal” outcome) or the “Death” form, the information will be presented in a summary table and a data listing.

16.3. LABORATORY EVALUATIONS

Results from the central laboratory will be included in the reporting of this trial for Serum Chemistry, Hematology and Urinalysis. A list of laboratory assessments to be included in the outputs is included in APPENDIX 5.

Presentations will use SI and US Units.

Quantitative laboratory measurements reported as “< X”, i.e., below the lower limit of quantification (BLQ), or “> X”, i.e., above the upper limit of quantification (ULQ), will be converted to X for the purpose of quantitative summaries, but will be presented as recorded, i.e., as “< X” or “> X” in the listings.

Qualitative laboratory urinalysis results measured by central laboratory will be classified to the categories “Positive” and “Negative” based on the central laboratory normal reference.

The handling of retests, unscheduled, and end of trial measurements is described in Section 6.3. However, laboratory values taken after the first dose of trial medication up to the end of a period (i.e. up to 10 weeks after the last dose of the trial medication) will be assigned to the treatment phase for evaluation. All available data will be listed.

The following summaries will be provided for laboratory data:

- Actual and change from baseline by visit (for quantitative measurements)
- Shifts from baseline category (Low/ Normal/ High) by visit (except for urinalysis)
- Shift from baseline category (Negative/ Positive) by visit (for urinalysis)
- Listing of subjects meeting abnormal criteria
- Proportion of possible Hy’s law subjects
- Proportion of possible Drug Induced Liver Injuries (DILIs)
- The time course of alanine aminotransferase (ALT), aspartate aminotransferase (AST) and total bilirubin (TBL) for all possible Hy’s law subjects, all parameters shown on a logarithm to base 10

Document: \\ieedc-
vnasc01\BIOSdata\Boehringer_Ingelheim\BI_695501\NVA96252\Biostatistics\Documentation\S
AP\BI1297.4 SAP FINAL v4.0_22MAY2019.docx

Author: Version Number: Final V4.0
Version Date: 22MAY2019

Template No: CS_TP_BS016 Revision 5
Effective Date: 01Apr2018

Reference: CS_WI_BS005

scale of the multiple of the upper limit of normal (ULN) (Y axis) versus days since treatment start (X axis).

- Scatter plots for Evaluation of Potentially Drug-Induced Liver Injury:
 - log ALT on the X axis and log TBL on the Y axis, both shown on a logarithm to base 10 scale of the multiple of the ULN
 - log AST on the X axis and log TBL on the Y axis, both shown on a logarithm to base 10 scale of the multiple of the ULN.

Baseline is described in section 6.2.

16.3.1. LABORATORY SPECIFIC DERIVATIONS

- Log ALT = logarithm to base 10 scale of the multiple of the ULN of ALT
- Log AST = logarithm to base 10 scale of the multiple of the ULN of AST
- Log TBL = logarithm to base 10 scale of the multiple of the ULN of TBL. Note: Bilirubin value instead of TBL will be used.
- Potential Hy's law categories:
 - Category 1: ALT or AST $\geq 3 \times \text{ULN}$ and TBL $\geq 2 \times \text{ULN}$ within the same sample
 - Category 2: TBL $\geq 2 \times \text{ULN}$ within 30 days after transaminase peak (ALT or AST $\geq 3 \text{ ULN}$)
- Potential Hy's Law subjects are defined as subjects with laboratory data in at least one Potential Hy's law categories at any time point of the trial.
- Drug induced liver injury (DILI):
 - Normal liver function at Baseline is defined as AST and ALT and Total Bilirubin values measured at baseline are each \leq respective ULN.
 - For post baseline visits:
 - Marked peak aminotransferase (ALT, and/or AST) elevations ≥ 10 fold ULN for all subjects with normal liver function at baseline.

Document: \\ieedc-vnasc01\BIOSdata\Boehringer_Ingelheim\BI_695501\NVA96252\Biostatistics\Documentation\SAP\BI1297.4 SAP FINAL v4.0_22MAY2019.docx

Author: Version Number: Final V4.0
Version Date: 22MAY2019

Template No: CS_TP_BS016 Revision 5
Effective Date: 01Apr2018

Reference: CS_WI_BS005

16.3.2. LABORATORY REFERENCE RANGES AND MARKEDLY ABNORMAL CRITERIA

Quantitative laboratory measurements will be compared with the relevant laboratory reference ranges in SI units and categorized as:

- Low: Strictly below the lower limit of the laboratory reference range.
- Normal: Within the laboratory reference range (upper and lower limit included).
- High: Strictly above the upper limit of the laboratory reference range.

16.3.3. OTHER SAFETY LABORATORY EVALUATIONS

16.3.3.1. Pregnancy test

Descriptive table will present pregnancy results for females by visit on SAF.

The pregnancy results will be listed as well.

16.3.3.2. Tuberculosis test

Descriptive table will present Tuberculosis (TB) test results by visit on SAF.

The TB test results will be listed as well.

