5.3.5 Other safety parameters

5.3.5.1 Tuberculosis assessment

A chest X-ray will be reviewed by the investigator or designee at Screening. If chest radiographs have been taken within 12 weeks of the Screening Visit then the chest radiographs do not need to be repeated (as long as they show no clinically significant abnormality and no signs or symptoms suggestive of lung disease that would exclude the patient from the trial). The results must be entered into the eCRF.

An IGRA (e.g., QuantiFERON[®]-TB Gold) will be used to assess TB status at Screening and, for patients who continue to the maintenance phase, at Visit 14 Week 24 (before switch from EU-approved Humira to BI 69550 and at EoT (Week 48 or earlier for patients who discontinued treatment during the maintenance phase). In the event of an indeterminate result at Screening, the test should be repeated. If a second indeterminate result is obtained then the patient must be excluded from the trial participation.

In the event of an indeterminate or positive result during the study, the test should be repeated and if a result is positive, then the patient will discontinue receiving the study treatment and followed up for safety. The patient will be referred to the specialist as required by local regulations.

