	to find the patients for the study participation		
	within a reasonable timeframe and therefore the		
	trial was redesigned to an exploratory trial.		
	Implementation of the updated statistical		
	considerations will allow achieving the study		
	objectives for the efficacy, as well as the		

09542349-05Trial ProtocolPage 91 of 93Proprietary confidential information © 2017 Boehringer Ingelheim International GmbH or one or more of its affiliated companies

	assessments of safety with the number of evaluable subjects decreased to 65 in each group and the total sample size of	
	approximately 130.	
Section to be changed	Flow Chart A, footnote 4	
Description of change	Text added: "TB test will be performed at	
P	 Week 24 before switch from EU-approved Humira to BI 695501, at EoT visit and may be performed" Flow Chart B: TB testing (IGRA) added on Visit 14, Week 24. 	
Rationale for change	Additional TB testing added on Week 24, before switching from Humira to BI 695501, to clarify whether the incidence of possible positive TB tests is linked to the reference or investigational product.	
Section to be changed	2224221.1	
Section to be changed Description of change	3.3.3, 4.2.2.1:1Exclusion criterion 8 updated to "Patients who	
Description of change	have received any biological treatment (other than TNF inhibitors), or investigational biological agent with the exception of infliximab within 6 months prior to Screening".	
	4.2.2.1:1 Line 6 and 7 updated accordingly	
Rationale for change	To emphasize that TNF inhibitors use is not allowed.	
Section to be changed	3.3.3	
Description of change	5.3.3 Exclusion criterion 10 updated to remove text "or are positive for anti-adalimumab antibodies at baseline"	
Rationale for change	To clarify that the results of the ADA are not available at the time of inclusion.	
~		
Section to be changed	5.2.1	
Description of change	Text updated in paragraph #3: "The patient is required to keep a symptom diary for 4 of these 8 variables (number of liquid stools, abdominal pain, general well-being, and use of antidiarrheal drugs) for 7 consecutive days before each CDAI evaluation." Paragraph #4: The day of bowel preparation for colonoscopy and the day of colonoscopy will be	

[figure not shown]
09542349-05Trial ProtocolPage 92 of 93Proprietary confidential information © 2017 Boehringer Ingelheim International GmbH or one or more of its affiliated companies

	excluded from the CDAI assessment.	

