6.3. RETESTS, UNSCHEDULED VISITS AND EARLY TERMINATION DATA

In general, for by-visit summaries, data recorded at the nominal visit will be presented. In the case of a retest, an unscheduled assessment will be created. For laboratory assessments as described in APPENDIX 5, the latest available measurement within acceptable timeframe after the planned assessment will be used for by-visit summaries. Unless assigned to a planned visit number, unscheduled measurements will not be included in by-visit summaries.

Treatment early termination data will be included in End-of-Treatment visit in by-visit table summaries and by-visit graphs, according to the protocol.

Listings will include scheduled, unscheduled, and retest data as collected in the eCRF database.

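### SAP 16.3.3.2 plans a by-visit TB table that does not summarise whether new positives arose on Humira or on BI 695501, the question the Week 24 test was added to address

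*SAP*

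**What the plan says.** Protocol 11.2 (Global Amendment 2, 12 Dec 2017) records the schedule change as "Flow Chart B: TB testing (IGRA) added on Visit 14, Week 24". It gives the reason as "to clarify whether the incidence of possible positive TB tests is linked to the reference or investigational product".

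Protocol 5.3.5.1 requires a repeat after an indeterminate or positive on-study result: "if a result is positive, then the patient will discontinue receiving the study treatment and followed up for safety". The same section places the last scheduled test "at EoT (Week 48 or earlier for patients who discontinued treatment during the maintenance phase", so a patient who stops during maintenance is due a further test.

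SAP 16.3.3.2 has two sentences on analysis: "Descriptive table will present Tuberculosis (TB) test results by visit on SAF" and "The TB test results will be listed as well". It does not define a new positive, the denominator, how a repeat counts, or what happens when the Week 24 result is missing.

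SAP 6.3 adds: "Treatment early termination data will be included in End-of-Treatment visit in by-visit table summaries and by-visit graphs, according to the protocol". It also makes each retest an unscheduled assessment and keeps unscheduled results out of by-visit summaries unless they carry a planned visit number. SAP Appendix 1 names two treatment groups for tables, BI 695501 and Humira.

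**The concern.** The Week 24 test was added for attribution, so one would expect the SAP to say how positives are attributed. A table by visit and treatment group shows test status at each visit. It does not show in which interval, and so on which product, a patient first became positive.

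This matters most in the Humira group, where every patient still on treatment moves to BI 695501 at Week 24. A positive shown at EoT in that group may belong to time on Humira, to time on BI 695501, or to neither with any confidence. A safety reader comparing the EoT rows could credit the wrong product with a conversion.

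**Working it through.** The documents give no figure for TB results, so there is nothing to reproduce. The check traces the rules and then illustrates their effect with assumed counts.

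**1. Who can be positive in the Humira group's EoT row**
- Patients positive at Week 24. They stop treatment (Protocol 5.3.5.1), are due an EoT test, and their early-termination data go to the EoT row (SAP 6.3). They reappear if the EoT test is done and still positive.
- Patients negative at Week 24 who become positive after the switch.
- Patients who stopped on Humira between Week 4 and Week 24, whose only on-study scheduled test is at EoT.
- Switched patients with no Week 24 test, including any who passed Week 24 before Amendment 2 took effect.

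Nothing in SAP 16.3.3.2 separates these four.

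**2. Coverage of the Week 24 test**
Week 24 is Day 169, which is 168 days after Day 1. 12 Dec 2017 minus 168 days is 27 Jun 2017. Anyone randomised before about that date passed Week 24 before the amendment was dated, and the cut-off is later where approval took longer. The original protocol is dated 30 May 2016, 393 days earlier, but that is not a first-enrolment date. The share affected is not given and could be zero. The pooling in step 1 does not depend on it, because those who stopped between Week 4 and Week 24 also lack the test.

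**3. Status against new positives**
Let k patients be positive at Week 24 and still positive at EoT, and let m be new at EoT. The rows show k and k + m. Their sum is 2k + m, while the number of distinct patients is k + m.
- k = 1, m = 1: rows 1 and 2, sum 3, distinct patients 2.
- k = 2, m = 1: rows 2 and 3, sum 5, distinct patients 3.

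An interval table would show k and m.

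**4. Denominator**
The SAF includes Week 4 non-responders, who never reach Week 24. Assume 65 per arm, 2 positives at Week 24, no losses between Week 4 and Week 24, and 25% to 100% of maintenance patients tested.
- SAF denominator: 2/65 = 3.1%.
- 80% entering maintenance (Protocol 7.7): 0.80 × 65 = 52, of whom 13 to 52 tested. 2/13 = 15.4% and 2/52 = 3.8%.
- 54.1% entering maintenance (pooled rate in Protocol Appendix 10.3): 0.541 × 65 = 35.2, of whom 8.8 to 35.2 tested. 2/8.8 = 22.7% and 2/35.2 = 5.7%.

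SAP Appendix 1 asks for a row n or a footnote when the denominator is not the population count, but 16.3.3.2 does not say which denominator applies.

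**5. The confirmatory repeat**
SAP 6.3 uses the latest available value only for the laboratory tests in Appendix 5, and TB is not listed there. A repeat without a planned visit number is therefore left out. The table could show a first positive that was negative on repeat, or an indeterminate result that was positive on repeat.

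**6. Would the SAP's periods solve it?**
Section 16 refers to overall and Period output for safety. If the adverse-event wording in 16.1.1.1 were applied to TB, Period 1 ends before the date of the Week 24 visit and Period 2 starts on it. A Week 24 positive would then fall in Period 2, although Flow Chart B puts assessments before dosing and 5.3.5.1 puts this test before the switch.

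**The case against.** A reader might infer that the table double-counts Week 24 positives. It does not. Each row counts a patient once, and showing a persistent positive at two visits correctly describes status. An error arises only if rows are added or the EoT row is read as new events, and the SAP asks for neither. Recurrence also requires an EoT test that is done and still positive.

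A reader might also infer that the amendment's question goes wholly unanswered. That is too strong. With columns by treatment group, the Week 24 row compares Humira with BI 695501 before anyone has switched, among those tested. The listing includes retests and Study Day, so in a trial of about 130 patients each sequence can be traced by hand.

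Nor do the documents support the inference that most patients lack a Week 24 test: they give no enrolment figures, and no SAP change could recover missing tests. The table templates are not visible here, so a suitable layout cannot be excluded. Finally, TB conversion is not among the listed primary or secondary endpoints, and safety analyses are descriptive.

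All of this limits the size of the point. It leaves two gaps: the post-switch half of the question has no specified summary, and the SAP text does not define denominators, confirmation or the handling of missing Week 24 tests.

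**Conclusion.** The point holds in a limited form. SAP 16.3.3.2 specifies a status-by-visit table and a listing, and neither summarises new positives by the product in use when they arose. The Week 24 row is informative before the switch. The Humira group's EoT row can mix four sources that the table does not separate, and the confirmatory repeat may be missing from it.

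This assumes that the table uses the two treatment groups of SAP Appendix 1 and that retests carry no planned visit number. The number of patients affected cannot be derived from the documents, and the counts and percentages above are illustrations. Severity is low: descriptive safety output in an exploratory trial, with no effect on the primary or secondary efficacy results.

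**What to change.** Keep the by-visit table, state n tested at each visit, and add to SAP 16.3.3.2 a table of new confirmed positives per interval:
- Screening to Week 24, or to EoT if treatment stopped earlier, under the randomised product.
- Week 24 to EoT, under BI 695501, by original arm.
- Denominator: patients negative at the start of the interval with a result at its end.
- Count each patient once, at the first positive confirmed under the repeat-test rule in Protocol 5.3.5.1, and state how repeats and indeterminate results enter the table.
- Treat the pre-dose Week 24 test as pre-switch.
- Show EoT positives in switched patients with no Week 24 test on a separate 'not attributable' line.

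One related inconsistency affects who appears at EoT. Flow Chart A marks a TB test at EoT, while Protocol 6.2.2 says it is not required for patients stopping before maintenance. These passages must be reconciled.

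The cost is one extra descriptive table from data already collected, with smaller denominators in each interval. It shows when positives arose, not what caused them.
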